Demographics Information on participants' race, gender, sexual orientation, OEF/OIF/OND status (MSI), marital status, employment status, income, and education will be collected. Contact information and housing status, address, phone number, e-mail (if applicable) and type of living arrangement will also be collected.

Analysis plan. The project's data management and analysis will be supervised by [name], who received advanced biostatistics training during her Ph.D. in public health. Tests for linearity, independence, missingness, and distributional assumptions will be conducted on key variables. Distributions will guide modeling decisions and normalizing transformations will be used when appropriate.

Although we expect that randomization will balance the groups, we will validate randomization by comparing groups on key variables potentially related to outcomes. If we identify significant group differences, we will adjust for these variables in models. The EUC condition will be designed to be equal-attention, but we will examine potential associations of the outcomes with length of session in sensitivity models.

Mixed effects regression models (described below) will allow the use of data from all participants, including those with incomplete follow-up, and provides unbiased parameter estimates under the missing-at-random assumption.¹⁰² If the missing-at-random assumption is untenable, we will handle missing data with a pattern mixture model. Where we have missing data on individual variables for more than 15% of observations, we will impute using SAS PROC MI and PROC MIANALYZE to combine the results of PROC MI.

Generalized linear models (GLMs) and generalized linear mixed-effects models (GLMMs). We will assess treatment effects by using GLMs to examine differences between the intervention and EUC groups at specific assessment waves and GLMMs to examine the primary dependent measures over the study period as a whole. GLMMs have the advantage of: 1) adjusting variances for correlated data (i.e., repeated measures); 2) allowing time-varying independent variables; and 3) allowing subject-specific inferences. The link function for GLMs and GLMMs will be based on the distribution for each outcome. We will use procedures SAS PROC MIXED for continuous variables and PROC GLIMMIX for dichotomous and count data.

Aim-specific analyses. All hypotheses will be planned a priori. All analyses will use two-sided tests.

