Aim 1 analyses. Hypothesis 1: Participants randomized to the intervention condition will report fewer overdose risk behaviors than EUC participants at follow-up. The overdose risk behavior is conceptually a composite count of number of behaviors. However, prior to initiating modeling, we will examine the distribution of responses to individual items on the overdose risk behavior assessment as well as the distribution of the overall composite count. Primary analyses will consist of GLMs to examine group (Intervention vs. EUC) as the primary independent variable at each time point and a GLMM to examine the average effect of the intervention over all assessments. If GLM findings suggest that the impact of the intervention may vary by assessment period, this will be examined using a time by group interaction term.

Aim 2 analyses. Hypothesis 2a: Participants randomized to the intervention condition will have lower average MEM/day doses and MPRs than EUC participants over follow-up. Hypothesis 2b: Participants randomized to the intervention condition will report lower levels of aberrant OA use than EUC participants over follow-up. Aim 2 dependent variables will include both objective measures based on pharmacy data and self-reported aberrant use. Prescribed OA dose will reflect escalating doses (likely due to patient request) and high total doses after combining regularly scheduled and "as needed" OAs.¹² An MPR⁸² greater than 1 identifies potential overuse based whether new fills frequently occur before the days supplied by a prior fill have elapsed. The distribution of the daily dose, MPR, and COMM scores will be examined to select appropriate models. The same analysis strategy used to test intervention effects in GLMs and GLMMs for Aim 1 will be used for the dependent variables in Aim 2.

Secondary aim 1 analyses. Hypothesis 3: Participants randomized to the intervention condition will have fewer non-fatal overdoses, fewer injuries and other OA-related adverse events, and better OA storage and disposal behaviors and better functioning than EUC participants. Analysis will follow the general GLM and GLMM framework used in the Aims 1 and 2 analyses, but a survival analysis approach using Cox proportional hazards regression modeling will also be used to examine time-to-event data (non-fatal overdoses and emergency department visits).

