Secondary Aim 2 analyses. Hypothesis 4a: The effect of the intervention on overdose risk behaviors and OA use will be mediated by post-intervention self-efficacy and motivation to change. Hypothesis 4b: OIF/OEF/OND status and baseline psychiatric distress will moderate the effect of the intervention on overdose risk behaviors and OA use. Mediators: In further analysis of the GLMs and GLMMs developed for Aims 1 and

2, we will include potential mediators in additional models and examine changes in effect size for the group indicator. Following the recommendations of Preacher and Kelley¹⁰³, we will use a κ^2 statistic to estimate the effect size and conduct significant testing of the mediation. *Moderators*: An interaction effect between each hypothesized moderator and the group indicator (intervention vs. EUC) will be specified in separate GLMs. For longitudinal analysis, we will examine baseline moderator by group interactions in GLMMs.

Additional analyses. We will examine descriptive statistics of the “perceived satisfaction and utility” measure from the post-test for further refinement of the intervention materials for follow-up. Descriptive statistics will also be used to examine differences between those who participated and those who refused participation of select characteristics. The focus group interviews conducted with prescribers will be entered into NVivo 10. [name] and the coordinator will independently read transcripts and use an iterative process to develop a coding scheme. Final codes will be grouped conceptually into meaningful themes and sub-themes. We will also calculate the number needed to treat to prevent one adverse event and amount of therapist time needed to prevent one adverse event.

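### Kappa-squared is the only test named for mediation, but it cannot be negative, so Hypothesis 4a needs a test of the signed indirect effect

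*Combined protocol and SAP*

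**What the plan says.** Hypothesis 4a (Secondary Aim 2 analyses) states that the intervention's effect on overdose risk behaviors and opioid use "will be mediated by post-intervention self-efficacy and motivation to change". Two steps are given.

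- In the models built for Aims 1 and 2, "we will include potential mediators in additional models and examine changes in effect size for the group indicator". No test or threshold accompanies this step.
- Citing a methods paper on effect sizes for mediation, the plan will use a kappa-squared "statistic to estimate the effect size and conduct significant testing of the mediation".

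No bootstrap, interval type, null value or decision rule is given for kappa-squared. No test or interval is named for the indirect effect itself.

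On the outcome models, the Analysis plan says "The link function for GLMs and GLMMs will be based on the distribution for each outcome", and assigns "PROC GLIMMIX for dichotomous and count data". The Aim 1 outcome is described as "conceptually a composite count of number of behaviors". The Aim 2 outcomes are dose in MEM/day, MPR and the COMM score, with models to be chosen after their distributions have been examined.

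**The concern.** On the plain reading, one statistic serves as both effect size and significance test. Kappa-squared is a ratio whose numerator and denominator share a sign, so it is never negative. A hypothesis of no mediation then sits at the edge of its range, and an interval formed from percentiles of its resampling distribution lies wholly above zero whether or not mediation exists. An analyst who followed the text and took the familiar percentile bootstrap would have a test that cannot fail to reject.

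A second problem is independent of the first. Kappa-squared is computed from the variances and covariances of arm, mediator and outcome in a linear model. If the overdose risk behavior (ORB) count is fitted with a log link, no kappa-squared belongs to that model.

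At stake is the claim that self-efficacy and motivation carry the effect, which the protocol expects to inform theoretical models of brief interventions.

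**Working it through.** **Inputs from the documents.** Analysed sample 360, 180 per arm; two-sided alpha 0.05; mean count 1.9 (Power analysis). Pilot SD of the count 2.0 (Measures, Overdose Risk Behaviors).

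**Assumed inputs.** The standard definition of kappa-squared; path sizes a (arm to mediator) and b (mediator to outcome) of 0 or 0.3; no direct effect of arm.

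**The plan's own figures.** The documents give no figure for mediation. The stated 80% power figures reproduce closely, which confirms how the inputs were read.

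- Continuous, effect size 0.30: 0.30 × √(180/2) = 2.846; 2.846 − 1.960 = 0.886; power 81.2% (81.0% with the t distribution).
- Poisson count, rate ratio 0.80: SE = √[(1/1.9 + 1/1.52)/180] = 0.0811; |ln 0.80|/SE = 0.2231/0.0811 = 2.751; 2.751 − 1.960 = 0.791; power 78.6%.

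**Definition.** With X = arm, M = mediator, Y = outcome, and s for sample variances and covariances:

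- a = s_XM / s_XX
- b = (s_MY s_XX − s_XM s_XY) / (s_XX s_MM − s_XM²)
- limit of a, A = [s_MY s_XY ± √(s_MM s_YY − s_MY²) √(s_XX s_YY − s_XY²)] / (s_XX s_YY), taking + if a > 0 and − otherwise
- limit of b, B = ± √(s_XX s_YY − s_XY²) / √(s_XX s_MM − s_XM²), with the sign of b
- kappa-squared = ab / (A B)

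A has the sign of a, because the observed a lies within its own limits, and B has the sign of b. The ratio is therefore never negative.

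**Simulation.** 400 trials per setting, 1,000 bootstrap resamples each. Outcomes were normal, Poisson with mean 1.9, or negative binomial with shape 1.9²/2.1 = 1.72, which gives variance 1.9 + 2.1 = 4.0 and SD 2.0 at mean 1.9. For counts, both ab and kappa-squared were computed from the linear covariances. Mediation is absent whenever a or b is zero. The three percentage columns show how often the 95% interval excluded zero.

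| Outcome | a, b | Kappa-squared, percentile | Kappa-squared, Wald | Signed ab, percentile | Median kappa-squared |
|---|---|---|---|---|---|
| Normal | 0, 0 | 100% | 0% | 0% | 0.0013 |
| Normal | 0.3, 0 | 100% | 1.5% | 4.5% | 0.0044 |
| Normal | 0, 0.3 | 100% | 5.5% | 6.75% | 0.0103 |
| Poisson | 0, 0 | 100% | 0% | 0.25% | 0.0009 |
| Poisson | 0.3, 0 | 100% | 1.0% | 2.25% | 0.0048 |
| Poisson | 0, 0.3 | 100% | 5.0% | 4.75% | 0.0142 |
| Neg. binomial | 0, 0 | 100% | 0% | 0.5% | 0.0013 |
| Neg. binomial | 0.3, 0 | 100% | 0.75% | 4.25% | 0.0055 |
| Neg. binomial | 0, 0.3 | 100% | 3.75% | 4.25% | 0.0092 |
| Normal, true mediation | 0.3, 0.3 | 100% | 77.5% | 80.0% | 0.0415 |

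The Wald interval is kappa-squared ± 1.96 bootstrap SE. The smallest bootstrap kappa-squared in any null setting was about 9 × 10⁻¹⁰, still above zero. The simulation error of a 5% rate with 400 trials is √(0.05 × 0.95/400) = 1.1 points, so 6.75% is compatible with 5%.

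A separate simulation of 300 trials with 400 resamples used an overdispersed count with mean 1.9. The kappa-squared percentile interval excluded zero in 100% of trials in two null settings; the interval for the indirect effect did so in 5% (no arm effect on the mediator; mediator effect −0.2 on the log count) and 4% (mediator shifted by 0.3 SD; no effect on the outcome).

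**The case against.** The strongest reply is that the plan never specifies an interval. The 100% figure belongs to the percentile bootstrap and only restates that a positive quantity has positive percentiles. With a symmetric Wald interval, kappa-squared rejected in at most 5.5% of null trials and lost little power under true mediation (77.5% against 80.0%). The sentence can also be read as kappa-squared for effect size plus a separate, unnamed test, and the procedure recommended in the cited methods paper cannot be seen here. Kappa-squared near 0.001 to 0.014, as under the null settings, would look negligible to a sensible reader. For outcomes modelled as continuous, the linear definition is no obstacle.

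All of this stands, and it limits the claim. A reader might infer that Hypothesis 4a is bound to be declared supported whatever the data show. The documents do not support that, because they fix neither the interval nor the decision rule. A reader might infer that the linear-model basis makes the interval exclude zero. It does not; non-negativity alone does. A reader might also fault the step that watches the group coefficient, on the ground that logit coefficients shift when a non-mediator is added. No binary outcome is stated for Hypothesis 4a, so that argument has no target here.

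The reply does not supply a test. If kappa-squared is the test, its validity turns on an unstated choice. If a separate test was meant, none is named. The same edit answers both.

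**Conclusion.** The point holds in limited form. Kappa-squared as named is not a sound test of Hypothesis 4a: with no mediation, the false-positive rate runs from about 0–5.5% to 100% according to an interval method left open, while a percentile interval for the signed indirect effect gave about 0–7%. The 100% depends only on the standard definition of kappa-squared and a percentile-type interval. The other rates also depend on the assumed path sizes and outcome distributions.

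The lack of a counterpart for the ORB count is conditional as well. A log link is likely for a count, but the plan leaves the link to the observed distribution and allows normalizing transformations.

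The change is worth making and goes beyond adding detail, since a stated statistic should be replaced as the test. The primary analyses, the sample size and the moderator analyses are untouched.

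**What to change.** In the Secondary Aim 2 analyses, make the signed indirect effect the quantity tested, with a percentile-bootstrap 95% interval that resamples participants. Mediation is supported only if that interval excludes zero (one, on the ratio scale) in the hypothesised direction.

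- Outcomes modelled as continuous (possibly MEM/day, MPR and COMM): the product of coefficients, ab.
- ORB count, if fitted with a log link: an indirect effect on the rate-ratio scale. With a linear, normal-error mediator model and no arm-by-mediator interaction, this is exp(ab) in the GLM.
- Kappa-squared: descriptive only, for linear outcomes, with no significance claim.
- Change in the group coefficient: descriptive only.

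Adjusting for baseline values of mediator and outcome is an optional refinement. The cost is a few sentences in the analysis plan and modest programming. No new data are needed: the measures table already schedules behavioral intentions and self-efficacy at baseline, post-intervention and follow-up.

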Efforts are underway to change opioid prescribing behavior, but concurrent strategies are needed to address patient behaviors that increase opioid overdose risk. Overdoses result from a range of behaviors, including taking more than prescribed, using multiple substances with synergistic effects, and injecting/snorting crushed pills to get high. Factors such as having a mental health condition have been found to increase risk of overdose among Veterans receiving opioids for pain.⁸ Given the range of risk behaviors and relevant patient factors, tailored opioid overdose risk reduction strategies are urgently needed. Motivational enhancement (ME) is an evidence-based strategy that uses tailoring to enact behavior change through improving self-efficacy and motivation.^{9,10} Recent VHA initiatives to increase behavioral health providers in primary care, such as Primary Care-Mental Health Integration (PC-MHI), provide a clear opportunity to deliver ME interventions to the many patients treated for long-term pain in primary care. Although the impact of ME on overdose risk behavior is unknown, the use of an ME approach to reduce overdose risk behaviors is potentially well-suited to the context of long-term opioid pain care, when total and immediate discontinuation of opioid use is often unfeasible.

The proposed Prescription Opioid Safety Trial (POST) study will be a randomized controlled trial of a brief, tailored ME intervention that incorporates cognitive behavioral strategies to increase pain coping and is aimed at reducing patients' overdose risk behavior. The study will recruit 450 patients from primary care clinics at the VA Ann Arbor Healthcare System. Patients with long-term opioid use, defined as treatment for at least 84 days covered within the last 90 days, who are prescribed opioid doses of 20 morphine-equivalent mg/day or greater (an indicator of overdose risk¹²) will be screened and recruited into the study. Participants will then be randomized to either the intervention ($n = 225$) or an enhanced usual care (EUC) condition ($n = 225$); both conditions will be delivered by PC-MHI therapists. Pharmacy records and patient self-report will be assessed at baseline and 3-, 6-, and 12-month follow-ups to measure key outcomes. The **specific aims** are:

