OAs Prescribed. We will determine prescribed OA regimen from pharmacy data using established methods¹² with standard morphine equivalency ratios.¹¹ The Medication Possession Ratio (MPR)⁸² will also be used to measure actual medication use/adherence by accounting for early and late refills. The MPR can identify patients who consistently refill early, an indication of overuse. OA therapy outside of VHA will be assessed and those participants who report being prescribed OAs by non-VHA care providers will be asked about formulation, dose, and prescribed schedule, and the dose and MPR will be adjusted accordingly. Pharmacy data will also be used to determine prescribed dose for the eligibility criteria of 20 MEM/day.

Aberrant OA Use. The Current Opiate Misuse Measure (COMM) is a 8-item self-report of recent aberrant use developed for, and validated in, patients receiving OAs.⁶⁵ Items include: getting medications from someone other than the prescribing physician, taking medications differently than prescribed, and taking for reasons other than pain. Patients report their past-month behavior on a five-point Likert scale ($\alpha = 0.86$).

Overdose Risk Behaviors. We have adapted items on overdose risk (ORB) from Strang and colleagues²⁶ by adding risk factors specific to OAs.^{12,18,33,83} This measure was developed with a national consortium of experts. Items include: high dose (more than 100 MEM/day); combining OAs with other substances; route of use; using alone; and returning to usual dose after a period of abstinence. In our pilot RCT, this measure was able to detect substantial between-subject variation, with participants reporting between 0 and 10 behaviors, 70% reporting at least one risk behavior, and a mean number of behaviors of 1.9 (S.D.=2.0).

Secondary Outcomes.

Non-Fatal Overdose Experiences: Established items will be used to assess non-fatal overdose (OESWA and OESWD).⁸⁴ For each overdose, we will assess the date, substances involved, intent (categories including “suicide attempt,” “did not want to die but did not care about the risks,” “accident, effect of drug was not expected,” and “unsure”), preceding events, and actions taken by others.

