Power analysis. All power analyses are conservative because they are based on a retention rate of 80%, n=360 (180 per condition), despite the fact that the methods will maximize analytic sample size by including individuals with partial follow-up data. All power calculations were based on two-sided tests with $\alpha=0.05$ and were conducted using G*Power software. We estimated power for GLMs for both count and continuous outcomes. For continuous outcomes, such as OA dose and aberrant use (Aim 2), 80% power is achieved to detect a standardized effect size of 0.30. For overdose risk behaviors (Aim 1), we assumed a Poisson distribution and a mean count of 1.9 (based on our pilot work) and found 80% power is achieved to detect an incidence rate ratio of 0.80 for the intervention compared to EUC. We extrapolate from the power calculations presented here for GLMs that power for outcomes in GLMMs will allow for detection of similar effect sizes. Thus, the proposed study has sufficient sample size to detect small to moderate effects.

DISSEMINATION PLAN

Several dissemination products will be developed during this study. We will finalize the intervention training manual and develop additional materials. We will create a video demonstration of the different components of the intervention, with multiple examples for each component in order to show how the intervention is tailored. These products and the computer aid will be shared with key central office stakeholders and made available to VHA clinicians. Additionally, these products will be ready to be used in a future hybrid type-1 implementation study using a stepped wedge design and informed by the Replicating Effective Programs model.¹⁰⁴ This study could examine factors that facilitate implementation as well as fatal and non-fatal overdose as an outcome by implementing the intervention with larger numbers of patients.

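### The 80% power claimed for Aim 1 rests on a Poisson count, but the plan's own pilot SD implies about 50% for the same single-wave comparison

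*Combined protocol and SAP*

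**What the plan says.** The Power analysis paragraph (Research Design and Methods) sets out the Aim 1 calculation: two-sided 0.05, a GLM, a sample "based on a retention rate of 80%, n=360 (180 per condition"), and for the count of overdose risk behaviors "we assumed a Poisson distribution and a mean count of 1.9 (based on our pilot work) and found 80% power is achieved". It concludes that "80% power is achieved to detect an incidence rate ratio of 0.80 for the intervention compared to EUC". It then extrapolates, without a separate calculation, that the mixed models (GLMMs) will detect effects of similar size. The paragraph opens with "All power analyses are conservative because they are based on a retention rate of 80"%.

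The Overdose Risk Behaviors entry under Measures describes the same instrument in the same pilot: a range of 0 to 10 behaviors, with "70% reporting at least one risk behavior, and a mean number of behaviors of 1.9 (S.D.=2.0").

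Under Aim 1 analyses, the primary analyses are group comparisons by GLM at each time point, plus a GLMM for the average effect over all assessments. The general analysis text says that observed distributions will guide the choice of model. It names no overdispersed count model.

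**The concern.** The power calculation takes the mean from the pilot and leaves out the SD reported beside it in the Measures section. The Poisson assumption fixes the variance at the mean, and the pilot variance is about twice that. The test then has less power than stated.

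This is the only power calculation made for the Aim 1 primary outcome. It supports the paragraph's closing claim that the sample is large enough for small to moderate effects. If true power at IRR 0.80 is near one half, a null result read against a claimed 80% would be wrongly taken as evidence against a 20% reduction.

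There is a second, conditional risk. If the analysis also used the plain Poisson model assumed for power, its standard errors would be too small and false positives would rise.

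**Working it through.** **Inputs.** From the Power analysis paragraph: 180 per arm, two-sided 0.05, control mean 1.9, IRR 0.80 (intervention mean 1.9 × 0.80 = 1.52). From Measures: pilot SD 2.0 (variance 4.0) and 70% with at least one behavior (30% zeros).

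**Is the pilot count Poisson?**
- Variance/mean = 4.0/1.9 = 2.105; Poisson requires 1.
- Zeros: Poisson gives exp(−1.9) = 15%, and the pilot has 30%. A negative binomial matched to mean 1.9 and SD 2.0 gives 28%, so the zeros and the SD agree with each other.
- The background text says the pilot randomized 203 people. If the figures come from them, the standard error of variance/mean under Poisson is about √(2/202) = 0.10. The excess of 1.1 is about 11 standard errors, so it is not sampling noise.

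**Test.** Wald test on the log rate ratio: power = Φ(|ln 0.80|/SE − 1.96), with |ln 0.80| = 0.2231.

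**Reproducing the plan (Poisson).** Var = (1/1.9 + 1/1.52)/180 = 0.00658; SE = 0.0811; z = 2.75; power 78.6%. Other variance conventions give 78.9% to 81.7%. The stated 80% is therefore correct under its own assumption.

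**With the pilot SD.**
- Negative binomial: k = (4.0 − 1.9)/1.9² = 0.582. Var = (1/1.9 + 1/1.52 + 2k)/180 = 0.01304; SE = 0.1142; z = 1.95; power 49.8%.
- Quasi-Poisson: Var = 0.00658 × 2.105 = 0.01385; SE = 0.1177; z = 1.90; power 47.5%.
- Simulation of 20,000 negative binomial trials with a robust-variance test: 49.8%.

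| Quantity | Poisson | Negative binomial | Quasi-Poisson |
|---|---|---|---|
| Power at IRR 0.80, 180 per arm | 78.6% | 49.8% | 47.5% |
| Power at IRR 0.80, 225 per arm | 86.8% | 58.9% | 56.4% |
| IRR detectable with 80% power, 180 per arm | 0.80 | 0.72 | 0.71 |
| Analysable per arm for 80% power at IRR 0.80 | 187 | 371 | 393 |

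**Sensitivity.**
- Rounding: SD 1.95 to 2.05 gives 51.6% to 48.0% (negative binomial) and 49.4% to 45.6% (quasi-Poisson).
- If 1.9 is the average over both arms, power is about 52%.
- Averaging three follow-up waves without baseline multiplies the variance by (1 + 2r)/3, where r is the within-person correlation. The documents give no r. Assuming 0.3, 0.5 and 0.7, negative binomial power at 180 per arm is 76%, 67% and 59%.
- Adjusting one wave for baseline multiplies the variance by (1 − r²). For the same assumed values, power is 54%, 62% and 78%.

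**Plain Poisson analysis of such data.** Type I error = 2 × (1 − Φ(1.96/√2.105)) = 17.7%, and the simulation also gave 17.7%, against a nominal 5%.

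**The case against.** The strongest point is that 50% describes one analysis, not the whole design. The plan also names a GLMM over all assessments as primary, and averaging waves gives 59% to 76% under the assumed correlations. If that model also adjusted for baseline (variance factor (1 + 2r)/3 − r², equal correlations assumed), power would be about 84%, 86% and 94% for r = 0.3, 0.5 and 0.7. This stands as a limit on scope. It does not rescue the stated figure, which is itself for a GLM. The plan gives no correlation, and it adjusts only for variables found to differ between the groups.

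Second, the pilot dispersion may not transfer. The pilot was run in a non-VHA emergency department, its recall periods may differ from those at follow-up, and the trial oversamples high doses. The SD could move either way. But the plan takes its mean from this same pilot and gives no reason to accept the mean and reject the SD. To keep even 75% power, the SD would have to be about 1.45 or less.

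Third, the plan lets the data guide the model, so it is not committed to plain Poisson. This is correct, and the 18% type I error is therefore only conditional. But a suitable overdispersed model brings the power to about 50%, and plain Poisson loses control of type I error. Neither gives 80% power at 5%.

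Fourth, the word conservative is tied to retention and is true in that respect. The gain from 180 to 225 per arm is about 9 points, while overdispersion costs about 29. The label therefore misleads for Aim 1.

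**Conclusion.** The concern holds. The arithmetic behind the 80% is sound, but its distributional assumption contradicts the plan's own pilot data. For the comparison the plan describes (unadjusted GLM, one wave, 180 per arm, two-sided 0.05), power at IRR 0.80 is about 50%, and 80% power is reached only at an IRR of about 0.72. This rests on the pilot mean and SD applying to the trial's follow-up counts. The averaged-wave analysis does better, but without baseline adjustment it stays below 80% at 180 per arm for every correlation tried. No part of the plan allows for overdispersion in the power calculation. The statement should be corrected because the trial relies on it for its first primary aim.

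**What to change.** - **Power analysis:** restate Aim 1 using the pilot SD, as about 50% power for IRR 0.80 in a single-wave GLM with 180 per arm, or equivalently 80% power for an IRR of about 0.72. Say that this assumes the pilot dispersion carries over. If power is also claimed for the GLMM, give the assumed within-person correlation, and state whether baseline is in the model.
- **Conservative:** drop the word for Aim 1. At most, say that the 80% retention figure is cautious.
- **Aim 1 analyses:** name a negative binomial model, or a Poisson model with robust or scaled variance, so that the analysis and the power calculation match.

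The sample size can stay at 450. The cost is a reworded paragraph, one line in the analysis section, and a less favourable power statement. For scale, keeping 80% power at IRR 0.80 in the single-wave GLM would need about 371 to 393 analysable per arm, which is 928 to 984 randomized at 80% retention.
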